9.1.3. Randomization, Treatment Period, and Follow-up Period

9.1.3.1. Active Treatment Period: Weeks 0 To 52

Randomization: Week 0

Randomization will occur no later than 28 days after screening is initiated and will be designated as Week 0 and Day 1 of the study. At this visit, inclusion and exclusion criteria, concomitant medications, and laboratory evaluations should be reviewed and documented to determine that a subject remains eligible for participation in the study. All eDiary data collected since screening will be reviewed by clinic staff. Subjects must have at least 5 days of daily insulin use recorded within the 7 days immediately preceding randomization. If not, subjects/caregivers should be instructed to reschedule this visit to have at least 5 days of daily insulin usage recorded prior to the rescheduled randomization visit. Subjects will be randomly assigned as described in [Section 3.1](#) to receive study agent (golimumab or placebo). Subject weight and height will be obtained to determine dose and device.

After the predose PK/immunogenicity sample is drawn, the dose of study agent (golimumab or placebo) will be administered at the study site. Subjects should be monitored for at least 30 minutes following injection and be observed for any adverse reactions, including injection site reactions (See [Section 9.9](#)). Subjects/caregivers who want to participate in study agent administration “self-administration” outside of some study visits begin training on using the sponsor-supplied single-use injection devices (See details [Section 6.2](#)). Additional training on the eDiary and glucometer will be given as needed.

Future target dosing and study visit days will be calculated based on the day of initial dosing at randomization (Week 0) and will not be redefined later during the study. Therefore, the study staff are encouraged to discuss the study visit days with subjects/caregivers and consider this schedule to determine what might be the anticipated (ie, day of the week) for future dosing and

study visits. Specific study visits and study agent treatment windows and impact on study compliance is detailed in Section 7.

At this visit, subjects/caregivers will be supplied with a calendar with target dosing days and target study visit days that show dosing and visit windows (See Section 7.1.2).

Study Visits: Weeks 2 and 4

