9.8. Data to be Collected by Subjects

For this study subjects/caregivers will obtain and record a number of pieces of data to aid in endpoint analysis and compliance. The data will be collected using an eDiary that will be supplied by the sponsor to the subject/caregiver during the screening visit. Training on devices and what data is to be collected will be conducted by study-site staff at that visit, and at subsequent visits as needed. All data recorded in the eDiaries will be reviewed by study staff during study visits. For the open-label extension period, paper diaries instead of eDiaries will be provided.

- **Exogenous insulin administration.** Subjects/caregiver are to record the type and amount of insulin they have used during the 7-day period immediately preceding each study visit (see the [Time and Events Schedule](#)). This data will be used to calculate exogenous insulin use in units/kg/day. During the open-label extension period, subjects will be required to record 10 days of insulin use prior to each visit.
- **Hypoglycemic events.** Subjects/caregivers are to record information surrounding all BG measure measurement that are ≤ 70 mg/mL or of suspected hypoglycemia due to clinical symptomatology. Data including BG level, clinical symptoms (including but not limited to change in mental status or loss of consciousness), length of the event, therapies used to treat the event, and if assistance or medical care (including clinic, emergency room or hospitalization) was required for the event.
- **Study agent dosing.** For subjects/caregivers participating in self-administration they are to record study agent administration date, time, and anatomic location of the injection, person administering study agent, and if there are any complications associated with study agent administration.
- **Glucometer readings.**
 - Screening – Double-blind Week 104: Subjects/caregivers will be given a sponsor-supplied glucometer and supplies to self-monitor BG levels during the study. Subjects/caregivers may not use their own glucometers. Blood glucose readings should take place at least 4 times a day, ie, premeal and at bedtime, as needed and at any time of suspected hypoglycemia. Blood glucose readings from the provided glucometers will be electronically transmitted to the eDiaries provided or when BG levels ≤ 70 mg/mL during the double-blind period (Weeks 0 to 104).

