4. Comparing change from baseline in 4-hour C-peptide AUC directly by using non-parametric method such as rank analysis of covariance or ANCOVA model if the normality assumption holds.

Subgroup analysis of the primary endpoint by selected baseline characteristics will be presented. Details will be outlined in the SAP.

Secondary Endpoints

The major secondary endpoints listed below will be analyzed without multiplicity adjustment. Treatment effect in these endpoints will be estimated by the difference between the treatment

groups along with their associated 95% confidence intervals. The hypoglycemia event rate (number of hypoglycemia episodes per patient-year exposure) at Week 52 will be analyzed using a Poisson regression model. Change from baseline in insulin use and change from baseline in HbA1c will be analyzed by using an MMRM model. Additional details will be provided in the SAP.

1. Change from baseline in insulin use in units per kilogram body weight per day at Week 52.
2. Change from baseline in HbA1c at Week 52.
3. Hypoglycemic event rates (defined as BG levels of ≤ 70 , 55, and 35 mg/dL or clinical sequelae consistent with severe hypoglycemia in the absence of a BG reading) through Week 52.

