5.2.1.1. Multiplicity Adjustment for Testing Procedures

To control for multiplicity in the primary endpoint analysis and major secondary endpoint analyses, the hypothesis testing will be conducted in a hierarchical manner with the test on the primary analysis first and the tests on major secondary analyses next. The success of any major secondary analysis, i.e., $p\text{-value} < 0.05$, is contingent upon the success of the primary statistical analysis. Hochberg approach will be applied within major secondary endpoint analyses.

Nominal p-values will be reported for all other efficacy endpoints.

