5.4.2. Analysis Methods

5.4.2.1. The change from baseline in insulin use and HbA1c at Week 52

Change from baseline in insulin use and change from baseline in HbA1c will be analyzed with an MMRM model based on a restricted maximum likelihood (REML) approach. The analysis will be based on observed data and will include the fixed, categorical effects of gender, treatment, time, and treatment-by-time interaction, as well as the continuous, fixed covariates of baseline and baseline-by-time interaction. An unstructured covariance will be used to model the within subject errors. The treatment comparisons will be made between Golimumab and placebo at Week 52 and significance tests will be based on the difference between the Least-Squares means. No missing imputation will be applied. Treatment effect in these endpoints will be estimated by the difference between the treatment groups along with their associated 95% confidence intervals.

5.4.2.2. Hypoglycemia event rate at Week 52

The number of hypoglycemia events per subject from the first study agent administration through Week 52 will be compared between treatment groups by using a Poisson regression model with treatment as fixed factor, baseline HbA1c and age as covariates, and the study participation through week 52 in logarithm as an offset variable. Hypoglycemia event rate will be estimated for each treatment group and the ratio of the rates and its 95% CI will be estimated as well.

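### The hypoglycemia-rate model omits the subject's own pre-randomization episode rate, leaving some avoidable sampling variance (assumption-dependent, possibly small) but no bias

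*SAP*

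**What the plan says.** SAP 5.4.2.2 counts events "from the first study agent administration through Week 52" and compares the arms "using a Poisson regression model with treatment as fixed factor, baseline HbA1c and age as covariates", with "the study participation through week 52 in logarithm as an offset variable". No baseline hypoglycemia rate is derived; SAP 2.3 gives only a general baseline rule. The other two major secondary endpoints, change in insulin use and change in HbA1c (SAP 5.4.2.1), carry their own baseline and its interaction with time. So does the primary (SAP 5.3.2).

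The protocol plans to collect the relevant data before randomization:

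- Section 9.1.2 issues both devices at screening, for insulin use, glucose levels and hypoglycemic events.
- Section 9.8 states that "Subjects/caregivers will be given a sponsor-supplied glucometer and supplies to self-monitor BG levels during the study", under a sub-heading that starts at screening, with at least four readings a day.
- Section 9.1.3.1 says of the Week 0 visit: "All eDiary data collected since screening will be reviewed by clinic staff".
- The double-blind Time and Events Schedule marks both a glucometer review and a hypoglycemia event review at Week 0.

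On the status of the endpoint the documents differ. SAP 5.2.1.1 makes success on any major secondary "contingent upon the success of the primary statistical analysis" and adds that "Hochberg approach will be applied within major secondary endpoint analyses". Protocol 11.3 says: "The major secondary endpoints listed below will be analyzed without multiplicity adjustment".

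**The concern.** A subject's own recent episode rate is a natural candidate predictor of the later rate. It reflects testing habits, insulin regimen and individual tendency, which HbA1c and age may capture only in part. Randomization is stratified on C-peptide AUC alone, so nothing in the design balances hypoglycemia tendency between 54 golimumab and 27 placebo subjects. Under the SAP this endpoint is formally tested, so its precision matters. The adjustment would use data that the trial already plans to collect. It also has to be fixed in advance, because a covariate added after unblinding would look data-driven.

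**Working it through.** **The plan's own figure.** The only power figure in the documents is for the primary endpoint. The difference is ln(1.635) − ln(1.385) = 0.1659 and the SD is 0.215, with 54 and 27 subjects and two-sided alpha of 0.05. Power is 0.906 (normal) or 0.899 (noncentral t, 79 df), against the stated 90%, so it reproduces. For hypoglycemia the documents state no rate, dispersion, rate ratio or power. Apart from the arm sizes, the one-year counting period and the 28-day limit on screening, every input below is an assumption.

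**Step 1: the interval the planned model reports.** Ignoring covariates, the plain Poisson standard error of the log rate ratio is √(1/E₁ + 1/E₀), where E is the event total in an arm.

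- 26 events per subject-year: √(1/1404 + 1/702) = 0.046
- 104 events per subject-year: √(1/5616 + 1/2808) = 0.023

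Simulated model standard errors without and with the screening-rate term were 0.075 and 0.076 (10 events/year), 0.038 and 0.038 (40/year), and 0.024 and 0.024 (100/year). The covariate does not change the reported interval.

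**Step 2: the true sampling variance.** With log-normal subject rates of log-variance σ², it is approximately (e^σ² − 1)(1/54 + 1/27) + 1/E₁ + 1/E₀. For σ² = 0.4 and 40 events/year this is 0.492 × 0.0556 + 0.0014 = 0.0287, an SD of 0.169, against a reported standard error of 0.038. Over the tabulated grid below, the true SD without the covariate was 0.16-0.25 against model standard errors of 0.024-0.076. The Poisson test rejected a true null in 40-85% of runs unadjusted and 39-84% adjusted. The covariate does not cure overdispersion.

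**Step 3: what the covariate removes.** The covariate is the log of (screening episodes + 0.5) per monitored day. Two sets of null simulations with 54 and 27 subjects gave these reductions in the true variance of the log rate ratio:

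| Assumed setting | Correlation | Variance reduction |
|---|---|---|
| 10, 40 or 100 events/year; log-variance 0.4 or 0.7; 7, 14 or 28 days; 1,500 trials per scenario | 0.3 | 1-4% |
| same | 0.5 | 1-16% |
| same | 0.8 | 6-48% |
| 26-104 events/year; log-SD 0.5-0.8; 7-28 days | 0.3 | 0-4% |
| same | 0.6 | 1-19% |
| same | 0.8 | 6-42% |

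A 4% fall is worth 1/(1 − 0.04) = 1.04 times the subjects, and a 19% fall 1/(1 − 0.19) = 1.23 times. The first setting did not simulate HbA1c or age effects. To the extent that those predict the rate, the added gain is smaller.

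The gain is limited because the screening window holds few events: 26 × 7/365 = 0.5 expected at one end of the second setting and 104 × 28/365 = 8.0 at the other.

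**Step 4: the same loss seen as imbalance.** One SD of chance difference between arms in mean log baseline rate is log-SD × √(1/54 + 1/27) = 0.236 × (0.5 to 0.8) = 0.12 to 0.19. At correlation 0.6 this moves the log rate ratio by 0.071 to 0.113, or about 7-12% on the rate ratio. This is a conditional view of the variance in Step 3, not an additional harm.

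**Step 5: with a variance that allows for overdispersion.** A Pearson-scaled standard error does show the gain, for example 0.166 falling to 0.157 (40/year, σ² = 0.4, correlation 0.5, 14 days). Its type I error was 4-6% unadjusted and 5-8% adjusted.

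**The case against.** The strongest objection is that this is an optional refinement beside a larger problem. A reader might infer that the missing covariate widens the planned confidence interval or biases the comparison. Neither follows. The plain Poisson interval is set by event totals, and leaving out a prognostic covariate does not bias a randomized rate ratio. With a valid variance, chance imbalance is already covered by the interval. The more serious weakness in the same model is that neither document allows for overdispersion. All of this stands. It means the term is worth adding only together with a change of variance.

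A reader might also infer that the baseline rate is already in the database. The documents do not assure that. Protocol 9.1.2 describes the screening issue of devices as being for training. The electronic-transmission sentence in Protocol 9.8 names Weeks 0 to 104. The only completeness rule before randomization, 5 of 7 days in Protocol 9.1.3.1, covers insulin use. The window may also be well short of 28 days. At 0.5 episodes a week, one screening week is empty with probability e^−0.5 = 61%, and zero events over 7 versus 28 days gives covariate rates differing fourfold. This stands as a limit on the gain.

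A several-fold gain is a third tempting reading. Simulated variance ratios reach 4.3 only if each subject's rate is perfectly stable. That is hard to assume in subjects within 100 days of diagnosis whose insulin is being adjusted to HbA1c targets.

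It can also be said that insulin use and HbA1c are change-from-baseline endpoints, so their baseline is intrinsic, whereas an event rate has none defined. That weakens the argument from consistency. It does not remove the efficiency argument: the true variance essentially never rose in simulation, and Protocol 11.3 leaves model details to the SAP.

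**Conclusion.** The point holds in a limited form. The planned model leaves out a covariate that the trial intends to collect, and so leaves some avoidable sampling variance in the hypoglycemia rate ratio. The size is about 0-4% of the variance at a correlation of 0.3, 1-19% at 0.6 and 6-42% at 0.8. These figures rest wholly on assumed rates, heterogeneity, correlation and usable screening days, and the gain may be small. They describe true variance, not the interval that SAP 5.4.2.2 would report. The status of the endpoint as a gated test comes from the SAP alone and conflicts with Protocol 11.3.

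**What to change.** Before the Week 52 unblinding, amend SAP 5.4.2.2 as follows:

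1. Add the covariate log[(episodes from screening to Week 0 + 0.5) / days with eDiary or glucometer data in that interval]. Derive episodes with the 1-hour merging rule of SAP 5.4.1.2.
2. Give subjects with no monitored baseline days the overall mean, so that none are dropped. Keep baseline HbA1c and age.
3. Fit the model with a variance that allows for overdispersion: negative binomial, or Poisson with a scaled or robust variance, and a small-sample correction. A scaled or robust Poisson stays within the Poisson regression that Protocol 11.3 names; a negative binomial model should be recorded as a change from it.
4. Reconcile SAP 5.2.1.1 with Protocol 11.3 on multiplicity.

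The cost is one derived variable, one model term and a variance option, with no new data or visits. The completeness of screening records should be checked blind first. The downsides are short or incomplete screening records, a possibly small gain, and a type I error that can run slightly above 5% with a scaled standard error, which is the reason for the small-sample correction.

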5.4.2.3. Subgroup Analyses for Major Secondary Endpoints

The treatment difference of the major secondary endpoints by each subgroup factor listed in Section 2.3 will be explored and presented through forest plots. Subgroup analyses will not be performed on the endpoints defined for sensitivity analyses.

5.5. Other Efficacy Variables

Other efficacy variables include, but are not limit to the following:

C-peptide and proinsulin:

- MMTT-stimulated 4-hour C-peptide AUC over time.
- MMTT-stimulated 2-hour C-peptide AUC over time.
- peak MMTT-stimulated C-peptide over time.
- Fasting proinsulin over time.
- Fasting proinsulin /c-peptide ratio over time.
- The proportion of subjects with MMTT-stimulated 4-hour C-peptide AUC response over time

- The proportion of subjects with peak MMTT-stimulated C-peptide ≥ 0.2 pmol/mL over time.
- Time to peak MMTT-stimulated C-peptide <0.2 pmol/mL.

Hypoglycemia episodes

- Number of hypoglycemia episodes through Week 52 by quarter.
- Number of hypoglycemia episodes by American Diabetes Association (ADA) categorization⁴: symptomatic hypoglycemia, asymptomatic hypoglycemia, probable symptomatic hypoglycemia, and ADA-defined severe hypoglycemia.

Insulin

- Change from baseline in insulin use in units per kilogram body weight per day over time.
- Proportion of subjects with insulin free over time.

HbA1c

- Change from baseline in HbA_{1c} levels over time.
- Proportion of subjects reaching HbA_{1c} goal of $<7\%$ over time.
- Proportion of subjects reaching HbA_{1c} goal of $<6.5\%$ over time.
- Proportion of subjects with HbA_{1c} $<7\%$, $<6.5\%$ and $\leq 5.7\%$ at week 52.

Remission score

- Summary of Remission score over time
- Number of subjects in remission over time
- The proportion of subjects in remission among those in remission at baseline
- Remission duration among those in remission at baseline
- Number the subjects reached remission among those not in remission at baseline

Subjects with C-peptide response and in remission

- The proportion of subject with C-peptide response and in remission over time

T1D related auto-antibodies

- The proportions of subjects with positive T1D related auto-antibodies by count and type

5.5.1. Definitions

5.5.1.1. C-peptide responder

Subjects with decrease from baseline in 4-hour C-peptide AUC no more than 5% are defined as C-peptide responders.

5.5.1.2. Remission

Remission score is Insulin dose-adjusted HbA1c (IDDA1c). It is defined as the summation of HbA1c value in percent and 4 times the average daily insulin usage/kg. A remission score \leq is categorized as in remission.

5.5.1.3. Subjects with C-peptide response and in remission

Specifically, subjects with C-peptide response and in remission are referred to those with percent change from baseline in 4-hour C-peptide AUC \geq -5% and a remission score \leq 9 at a visit.

5.5.2. Analysis Methods

All analyses for other endpoints will be based on full analysis set unless otherwise specified.

For continuous endpoints, summary statistics (mean, standard deviation, median, IQ range, and range) will be presented by treatment group. For categorical endpoints, frequency counts and percentages will be presented by treatment group. Graphic presentations will be provided for some endpoints.

Treatment comparisons are presented for selected variables. Continuous endpoints will be analyzed using a mixed model repeated measures model to test the difference between treatment groups if deemed reasonable. Binary endpoints will be analyzed using a logistic regression in general. In case of complete separation, Chi-square test will be adopted. The hazard ratio for time to event data will be estimated using the Cox proportional hazards model and its 95% confidence interval will be calculated. The proportional hazards assumption will be verified with appropriate methods (e.g. log-minus-log plots) as part of the analysis. The survival curves will be estimated using Kaplan-Meier estimates.

Proportions of C-peptide responders at Week 52, subjects in remission at Week 52, and subjects who are C-peptide responders and in remission at Week 52 will be presented in subgroups defined by HLA-DR3 presence/absence and HLA-DR4 presence/absence. Forest plots will be created to represent treatment comparison in each of the subgroups.

There is no multiplicity adjustment for other efficacy endpoint analysis.

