1.2. Trial Design

This is a Phase 2a randomized, double-blind, placebo-controlled, parallel-group, multicenter, study of golimumab in children and young adults with new onset T1D. Confirmation of the autoimmune nature of T1D in subjects will be determined by positivity of at least one T1D-associated autoantibody. Subjects must also show evidence of residual endogenous β -cell function, defined by a C-peptide level of ≥ 0.2 pmol/mL from a 4-hour MMTT at study screening, and be able to be randomized within 28 days of screening and 100 days of diagnosis.

A diagram of the study design is provided below and as depicted in **Error! Reference source not found.**, approximately 81 subjects will be randomly assigned in a 2:1 ratio to receive golimumab or matching placebo therapy and be stratified based on a C-peptide AUC of < 0.66 pmol/mL or ≥ 0.66 pmol/mL from a 4-hour MMTT conducted at study screening. Following screening, subjects must be randomized within 28 days. Following randomization there will be a 52-week treatment period with study agent followed by a 52-week off-therapy follow-up period. Two planned database locks (DBLs) will occur, at Week 52 and at Week 104.

Figure 1: Schematic Overview of the Study

Efficacy assessments will be performed according to the Schedules of Activities. Serum samples for PK, immunogenicity, and exploratory assessments will be collected at the timepoints shown in the Time and Events Schedule in the protocol.

An independent Data Monitoring Committee (DMC) will be commissioned to continually assess the safety of study subjects. The DMC will evaluate an interim analysis based on 4-hour C-peptide AUC in response to an MMTT after at least 60% of subjects complete their Week 26 MMTT assessment. The primary goal of this interim analysis is to obtain an early read on treatment effect to facilitate planning of future studies.

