1.4. Sample Size Justification

This study is designed to enroll approximately 81 subjects in order to have sufficient power to detect a difference between the golimumab groups and the placebo group for the primary efficacy endpoint. The rationale for the study sample size is based on the hypothesis tests for the primary efficacy endpoint.

The sample size calculation is based on the primary endpoint, an MMTT 4-hour C-peptide AUC at Week 52. Due to skewed C-peptide AUC data, normalizing transformation of $\log(AUC + 1)$ is

applied for sample size assessment. The method has been well accepted and used in numerous clinical studies. Based on published data, a common standard deviation (SD) of log (AUC+1) of 0.215 is assumed, and the back-transformed means for 4-hour C-peptide AUC are assumed to be 0.385 and 0.635 for the placebo and golimumab groups respectively, ie the expected treatment difference (back-transformed) is 0.25. Based on these assumptions, with 81 subjects (54 on golimumab and 27 on placebo), there is 90% power to detect a treatment difference with a 2-sided significance level of 0.05 through a 2-sample t-test.

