5.2. Analysis Specifications

5.2.1. Level of Significance

Unless otherwise specified, all statistical testing procedures will be performed at a 2-sided significance level of 0.05.

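### The chi-square fallback for separated logistic models can overstate significance in sparse tables and gives no estimate for the planned HLA forest plots

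*SAP*

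**What the plan says.** SAP 5.5.2 (Analysis Methods, under Other Efficacy Variables) sets the default: "Binary endpoints will be analyzed using a logistic regression in general". The exception follows directly: "In case of complete separation, Chi-square test will be adopted". The section does not define separation, list covariates for the logistic model, choose between Wald and likelihood-ratio tests, or say whether the chi-square is continuity-corrected. It names no exact or penalised method.

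The same section asks for C-peptide response, remission, and both together at Week 52 to be shown by HLA-DR3 and HLA-DR4 status, with forest plots of the treatment comparison in each subgroup. SAP 5.5 lists further binary endpoints, including being free of insulin and peak C-peptide of at least 0.2 pmol/mL.

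On status, SAP 5.2.1 sets the default level: "all statistical testing procedures will be performed at a 2-sided significance level of 0.05". SAP 5.2.1.1 limits what these tests can claim: "Nominal p-values will be reported for all other efficacy endpoints".

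**The concern.** With treatment as the predictor, the maximum-likelihood odds ratio becomes infinite or zero as soon as one arm has no events or only events. This is the breakdown an analyst is likely to meet. Complete separation in the literal sense (no events in one arm, all events in the other) is implausible here. So the sentence has practical use only if it covers a single empty cell; if it does not, the SAP has no rule for the likely case.

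Empty cells are realistic. Freedom from insulin may be rare, and peak C-peptide of at least 0.2 pmol/mL may be nearly universal. SAP 5.2.2.1 generally counts a missing binary observation as non-response, which pushes counts towards zero. Expected counts in such tables are often below 5, where the chi-square approximation is weakest.

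Two things are at stake. A nominal p-value below 0.05 could be reported on one or two events. And a subgroup with an empty cell would have no estimate to plot.

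**Working it through.** **Inputs from the documents.** Group sizes are 54 and 27 (SAP 1.4), from 2:1 allocation (SAP 1.2). The level is 2-sided 0.05 (SAP 5.2.1). SAP 2.4 sets a minimum of 5 subjects per arm for subgroup analyses. **Assumptions.** The documents give no event rates for these endpoints, so a common true rate from 0.5% to 50% was scanned. HLA subgroup sizes are not given either. The chi-square is taken as uncorrected.

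**The plan's own figure.** The only stated operating characteristic is the power for the primary endpoint: "with 81 subjects (54 on golimumab and 27 on placebo), there is 90% power to detect a treatment difference". The log difference is ln(1.635) − ln(1.385) = 0.1659. With SD 0.215, the noncentrality is 0.1659 / (0.215 × √(1/54 + 1/27)) = 3.27, and the noncentral t gives 89.9%. The figure reproduces. The SAP states no error rate for the fallback.

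**Single tables.** For a/n1 vs b/n2 with N = n1 + n2, X² = N[a(n2−b) − b(n1−a)]² / [n1·n2·(a+b)(N−a−b)] on 1 df.

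- 0/54 vs 2/27: X² = 81 × 108² / (54 × 27 × 2 × 79) = 4.10, p = 0.043. The smallest expected count is 27 × 2/81 = 0.67. Fisher: both events fall on placebo with probability (27 × 26)/(81 × 80) = 0.108, which is the least likely split, so p = 0.108.
- 7/27 vs 0/14: X² = 41 × 98² / (27 × 14 × 7 × 34) = 4.38, p = 0.036. Fisher gives 0.075.
- 0/20 vs 1/5: X² = 25 × 20² / (20 × 5 × 1 × 24) = 4.17, p = 0.041. Fisher gives 5/25 = 0.20. One event crosses 0.05.

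| Table | Chi-square p | Fisher p |
|---|---|---|
| 0/54 vs 2/27 (same for 54/54 vs 25/27) | 0.043 | 0.108 |
| 7/54 vs 0/27 | 0.0503 | 0.089 |
| 8/54 vs 0/27 | 0.035 | 0.047 |
| 7/27 vs 0/14 (assumed subgroup) | 0.036 | 0.075 |
| 7/36 vs 0/18 (assumed subgroup) | 0.045 | 0.082 |
| 0/20 vs 1/5 (assumed subgroup) | 0.041 | 0.20 |

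**Type I error over all tables.** Every table was enumerated under equal binomial rates.

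- 54 vs 27: chi-square alone peaks at 5.2% (rate 18.5%). It is 4.0%, 3.9% and 3.7% at rates of 3%, 4% and 5%. The whole SAP rule (logistic test, with chi-square when a cell is empty) peaks at 4.9% with a Wald test and 5.4% with a likelihood-ratio test. Putting Fisher in place of chi-square leaves the Wald maximum at 4.9%.
- 20 vs 5: chi-square alone peaks at 9.0% (rate 5.5%); the whole rule with Wald reaches 8.2%.
- 30 vs 8: chi-square alone peaks at 9.7% (rate 3.5%); the whole rule with Wald reaches 8.7%.
- 18 vs 9, a 2:1 subgroup: chi-square alone peaks at 6.3%.

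**Estimates.** A chi-square test returns a statistic and a p-value. It supplies no odds ratio or interval for a forest plot, and the logistic odds ratio is not finite in the same table.

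**The case against.** The strongest objection is that the rule does little harm at the planned size. At 54 vs 27 its type I error is about 5% at most. For favourable events absent on placebo, chi-square and Fisher agree at 0.05 for every count: neither is significant at 7/54, and both are at 8/54. The discordant 0/54 vs 2/27 would count against golimumab on a favourable endpoint. All of this is correct. Discordance in golimumab's favour needs a near-universal endpoint (54/54 vs 25/27) or a smaller subgroup (7/27 vs 0/14).

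A reader might infer that the fallback nearly doubles the false-positive rate. Among tables with one empty or full arm at 54 vs 27, chi-square does reject 8.1%, 8.9% and 9.2% of the time at rates of 3%, 4% and 5%. But those figures condition on the pattern of the observed table. On the same conditioning, Fisher's valid test rejects 19% at a rate of 10%. They are not type I error rates.

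A reader might also take the text to invoke chi-square whenever a cell is empty. It says complete separation, and one empty cell is quasi-complete. In the literal case, 0/54 vs 27/27, the smallest expected count is 27 × 27/81 = 9 and the approximation is adequate. The defensible criticism is that the trigger is undefined. Finally, it cannot be said that the fallback discards covariates, because SAP 5.5.2 lists none.

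**Conclusion.** The point holds as a minor one. If the sentence covers an empty treatment-by-outcome cell, it prescribes a test that can report p < 0.05 in sparse tables where an exact test gives 0.075 to 0.20, and it leaves the HLA forest plots without an estimate in those tables. If it does not cover that case, the likely form of separation has no rule.

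Overall type I error is not inflated materially at 54 vs 27. Error near twice nominal appears only in small, uneven subgroups of sizes that SAP 2.4 would allow, and only at low event rates. Those rates, the subgroup sizes and the absence of a continuity correction are assumptions. With Yates' correction at 54 vs 27, chi-square alone peaks at 3.3%.

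The affected endpoints carry nominal p-values without multiplicity adjustment, so the primary and major secondary conclusions do not depend on this choice.

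**What to change.** Replace the fallback sentence in SAP 5.5.2 with a rule of this kind: if any treatment-by-outcome cell is empty (complete or quasi-complete separation), fit Firth penalised logistic regression with the same terms as the planned model and report the odds ratio with a profile-likelihood interval; where only a p-value is needed, use Fisher's exact test. Firth gives a finite estimate and interval, so every HLA subgroup that contains both outcomes can be plotted.

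The cost is one sentence and one software option. Fisher is somewhat conservative: at 54 vs 27 its type I error peaks at 3.6%.
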